Setting and Participants Patients ages 18+ years with symptomatic cholelithiasis or biliary colic who are a member of a racial or ethnic minority, not primary English speaking, from a low-income neighborhood or underinsured will be identified from the PCSL (see above) and Emergency Department (ED) discharges including referral to surgery. See **Figure** for exclusion criteria. After Institutional Review Board (IRB) approval, potential participants with a new ICD-10 code for symptomatic cholelithiasis or biliary colic seen by a PCSL provider between April 1, and June 30, 2023 will be identified. The diagnosis and discussion with the PCSL provider will be confirmed by chart review to ensure the patient is aware of their diagnosis. Then, patients will be recruited via the electronic health record. Nonresponses will be contacted by phone. If enrollment is lower than required, patients will be approached about participation at the time of the in-person PCSL or ED visit. Participation will be voluntary and informed consent will be obtained. For this pilot study, enrollment will proceed to a maximum of 25 per group. We anticipate between 2-37 eligible patients per week. Participants will receive an incentive of \$20 for participation. Demographics and clinical information will be collected in REDCap, a HIPPA-compliant, secure web application for building and managing online surveys and databases.

Exposure, Intervention Assignment, Covariates and Outcomes

Exposure: Assignment to telemedicine surgical consultation (vs. usual care) during the week of diagnosis of symptomatic cholelithiasis or biliary colic.

Intervention Assignment: Pragmatic randomization will be performed by group enrollment in alternating weeks.

Covariates: Participants will be followed for 6-months from enrollment. Data on patient attributes will include age, race, sex, insurance status, primary language and 9-digit zip code as a proxy for neighborhood income level. Clinical factors will be abstracted from the electronic medical record including comorbid conditions as defined in the Elixhauser Indices [28], bilirubin, liver function studies, ultrasound scan and CT scan results.

Outcomes: Primary outcome will be proportion of patients who undergo surgical consultation. Surgical consultation will be determined via chart review including care everywhere to

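### Aim 2 allocates arms by alternating weeks, a predictable rule, but calls it randomization, and no sentence says whether the diagnosis week or the enrollment week sets the arm

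*Combined protocol and SAP*

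**What the plan says.** Under Intervention Assignment, the Aim 2 plan states: "Pragmatic randomization will be performed by group enrollment in alternating weeks". The Exposure line just above it defines exposure as "Assignment to telemedicine surgical consultation (vs. usual care) during the week of diagnosis of symptomatic cholelithiasis or biliary colic". Elsewhere, the Scalability section says that patients will be randomized between the two visit types, while Overall Approach says only that two groups will be pragmatically assigned.

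Under Setting and Participants, a new diagnosis is identified and confirmed by chart review, and patients are then invited through the electronic health record. After that, "Nonresponses will be contacted by phone". There is a fallback: "If enrollment is lower than required, patients will be approached about participation at the time of the in-person PCSL or ED visit". On consent: "Participation will be voluntary and informed consent will be obtained". Size and accrual are given as "enrollment will proceed to a maximum of 25 per group" and "We anticipate between 2-37 eligible patients per week"; the power section targets 20 per group. Follow-up runs from enrollment: "Participants will be followed for 6-months from enrollment".

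The primary outcome is the proportion of patients who undergo surgical consultation. Data Analysis plans univariate comparisons. The power section names preliminary evidence of efficacy among the pilot's goals, beside recruitment and retention rates. The Project Abstract wants the results as preliminary data for a larger grant.

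**The concern.** Three things need separating.

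- **Label.** The mechanism is stated openly, but alternation is not a random sequence. A reader of the Scalability section alone would credit the design with a property it does not have.
- **Anchor.** Two adjacent lines point to different events. Under weekly alternation, a one-week gap between those events reverses the arm.
- **Knowledge of the arm at consent.** The supplied text does not say whether patients or recruiting staff know the arm when consent is sought.

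The outcome makes this matter. A patient's willingness to join a known arm is plausibly related to whether that patient will see a surgeon, which is the primary endpoint. The Limitations section treats refusal to see a surgeon as a problem whose magnitude the pilot has yet to gauge. Selection at entry is not removed by taking the outcome from chart review or by univariate tests. It could be read as a telemedicine effect, or could hide one, in the estimate used to plan the next study.

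**Working it through.** **No stated figure to reproduce.** The plan gives no number for the allocation method, so the check is mainly a reading of the text, followed by a labelled illustration.

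**Predictability.** The identification window under Setting and Participants is 1 April to 30 June 2023: 30 + 31 + 30 = 91 days, and 91 / 7 = 13 weeks. Strict alternation gives 7 weeks to one arm and 6 to the other. Once one week's arm is known, the other 12 follow.

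**Can the two weeks differ?** Chart review, the record invitation, phone calls to nonresponders and consent all come between diagnosis and enrollment. Take a patient diagnosed late in one week who is reached by phone early in the next:

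| Rule | Week that counts | Arm |
|---|---|---|
| Diagnosis week governs | First | That of the first week |
| Enrollment week governs | Second | The opposite arm |

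If the enrollment week governs, whoever times the call or the consent can determine the arm. If the diagnosis week governs, the arm is fixed before contact, and what remains is differential approach or consent with the arm known.

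**Is the fallback route likely?** At the low end of expected accrual, 2 × 13 = 26 eligible patients, fewer than the 2 × 20 = 40 targeted. In-person approach is therefore a realistic scenario. If it happens at the diagnosis visit, the two weeks coincide and timing cannot move the arm, but consent with the arm known is still possible.

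**Weight of one patient.** 1/20 = 5 points in an arm of 20; 1/25 = 4 points in an arm of 25.

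**Illustration of selection.** Assumptions, none from the documents: no true effect; underlying consultation rate p of 50% or 70%; in one arm only, patients who would attend consultation are r times as likely to consent as the others. The rate among those enrolled in that arm is p·r / (p·r + 1 − p).

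| p | r | Enrolled rate | Spurious difference |
|---|---|---|---|
| 50% | 1.25 | 0.625/1.125 = 55.6% | 5.6 points |
| 50% | 1.5 | 0.75/1.25 = 60.0% | 10.0 points |
| 50% | 2 | 1.0/1.5 = 66.7% | 16.7 points |
| 70% | 1.25 | 0.875/1.175 = 74.5% | 4.5 points |
| 70% | 1.5 | 1.05/1.35 = 77.8% | 7.8 points |
| 70% | 2 | 1.4/1.7 = 82.4% | 12.4 points |

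The sign depends on which arm is affected.

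**Sampling error for comparison.** The 95% half-width at 20 per group is 1.96·√(2p(1−p)/20): 1.96·√(0.50/20) = 31 points at 50%, and 1.96·√(0.42/20) = 28 points at 70%.

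**Effect on the test.** Summing binomial probabilities over all outcome pairs at 20 per group that reach two-sided 0.05, Fisher's test rejects in 2.9%, 4.9% and 11.2% of trials at p = 50% (r = 1.25, 1.5, 2), and in 3.1%, 4.6% and 8.6% at p = 70%.

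**The case against.** The strongest case on the other side has four parts.

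- **The rule is disclosed.** Intervention Assignment states the mechanism and the trial is called pragmatic, so nobody who reads that section is misled. This stands as to intent and makes the label a wording matter. It does not make a fixed rule random, and the Scalability section gives the label without the mechanism.
- **The anchor has a natural reading.** The Exposure line names the diagnosis week, and the assignment line names no competing week of enrollment. Counting follow-up from enrollment says nothing about assignment. This largely stands. A reader might infer that the plan contradicts itself or lets enrollment timing set the arm; the text supports neither. It supports only that no sentence links the two lines, so staff could apply them differently.
- **Concealment may be described elsewhere.** A reader might infer that the trial has no concealment, or that patients consent knowing their arm. The documents do not support that, since consent pages and figures were not available for this review. The point is therefore a question.
- **Harm is assumed, and this is a pilot.** The consent ratios are invented, every shift lies inside the half-width, and Fisher's rejection rate stays below 5% for ratios of 1.25 and 1.5. This stands: the documents do not show that bias will occur. But a confidence interval does not capture selection and more patients do not shrink it, so the harm would fall mainly on the estimate carried forward.

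**Conclusion.** The point holds in a limited form and should be fixed before enrollment. Two parts rest directly on the text, with high confidence: alternating weeks is a systematic rule labelled as randomization, and the governing week is not stated. Whether the arm is known when consent is sought is open.

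The size of any bias cannot be estimated from the documents. Under the assumed consent ratios of 1.25 to 2 in one arm, with underlying rates of 50% or 70% and no true effect, the spurious difference is about 4 to 17 points, against a half-width of 28 to 31 points at 20 per group.

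A reader might conclude that the pilot is invalid. That goes too far: estimating recruitment and retention, and the feasibility hypothesis (Hypothesis 2.1), do not depend on the allocation being random. What is exposed is the between-arm difference in surgical consultation, if it is used as preliminary evidence of efficacy.

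**What to change.** **Preferred.** Replace alternation with a computer-generated 1:1 list in permuted blocks, concealed from recruiting staff and released after consent. Change the Exposure line to *assigned consultation type*. The cost is protocol wording and one allocation list; the downside is that both visit types must be available every week.

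**If weekly allocation is kept:**

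- (a) State identically under Exposure and Intervention Assignment: *The arm is set by the calendar week in which the qualifying diagnosis was recorded, whatever week the patient is contacted or enrolls.* Define the first day of the week.
- (b) In Scalability and Intervention Assignment, call the design quasi-randomized allocation by alternating weeks, or randomize the order of weeks in small blocks.
- (c) Report the numbers eligible, approached and consented by arm, and give the between-arm difference with a 95% confidence interval as an estimate.
- (d) Add predictable allocation to the Limitations.

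This option costs little beyond wording and recruitment counts. It removes the ambiguity, but the allocation stays predictable if alternation is kept, and is only less so if the week order is randomized.

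**In either case,** the sponsor should say whether consent is obtained before the patient and the recruiting staff know the arm.

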ensure capture of visits outside of Penn Medicine. Secondary outcomes will include time to consultation, proportion to undergo cholecystectomy, time to surgery, and emergent/urgent vs elective operation.

Data Analysis Descriptive statistics will be performed. Univariate comparisons to test hypotheses will be performed using the chi-square test or Fisher's exact test for categorical data and t-test or Wilcoxon rank-sum for continuous data. Statistical analysis will be performed using STATA Version 17 (Stata Corporation, College Station, TX). Stratified analyses will be performed by race, ethnicity, primary language, median neighborhood income, and insurance status as permitted by sample size.

PRELIMINARY STUDY RESULTS and POWER CALCULATIONS

In addition to providing preliminary evidence of the efficacy potential of telemedicine surgical consultations, the goal of the pilot study is to estimate recruitment and retention rates and population variance of social vulnerability factors. Because we want to be powered to detect small effect sizes, ($0.1 \leq d < 0.3$) where d is the standardized difference, we will target enrollment of 20 participants per group to achieve a power of 80%, $\alpha=0.05$. [32]

Limitations

- The study focuses on patients already connected to primary care providers. Many patients with SV may not reach that point in the health system. However, in clinical practice at Penn Medicine it is not uncommon for patients to have insurance that allows primary care at our community sites without providing benefits for surgical care for nonemergency conditions. This approach to patient care exposes patients treated in our community to the excessive clinical and financial risks associated with emergency surgery. Because we will conduct an explanatory analysis of factors associated with surgical consultation and treatment, we will identify barriers to surgical health equity (e.g., insurance coverage) within our system. This will allow us to develop strategies to achieve health equity at the system level.

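### Aim 2 specifies no covariate-adjusted telemedicine effect; one pre-specified adjusted estimate using a binary insurance indicator would be a cheap addition to the unadjusted tests

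*Combined protocol and SAP*

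**What the plan says.** The Data Analysis paragraph of Aim 2 gives the method for the between-group hypotheses: "Univariate comparisons to test hypotheses will be performed using the chi-square test". Fisher's test is the named alternative for proportions, and continuous outcomes are to be compared by a t-test or a rank-sum test. Covariates enter the Aim 2 analysis in only one other place: "Stratified analyses will be performed by race, ethnicity, primary language, median neighborhood income, and insurance status as permitted by sample size".

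The Covariates paragraph of Aim 2 collects much more: "Data on patient attributes will include age, race, sex, insurance status, primary language and 9-digit zip code as a proxy for neighborhood income level", and from the medical record "comorbid conditions as defined in the Elixhauser Indices [28], bilirubin, liver function studies, ultrasound scan and CT scan results". Neither list is given a role in estimating the telemedicine effect. Comorbidity, age, sex and laboratory values are not among the strata.

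Allocation is described under Intervention Assignment: "Pragmatic randomization will be performed by group enrollment in alternating weeks". The target is 20 per group and the maximum is 25. Multivariable regression to handle confounding is planned in the Aim 1 Analytic Strategy and nowhere in Aim 2.

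The Limitations section describes patients with "insurance that allows primary care at our community sites without providing benefits for surgical care for nonemergency conditions" and says that this is not uncommon.

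**The concern.** The primary outcome is whether a surgical consultation takes place. The protocol itself points to insurance as a barrier to surgical care, so insurance is a plausible predictor of that outcome. With about 20 patients per group, the arms may differ noticeably in insurance mix. An unadjusted difference in proportions carries the consequence of that mix into the realised estimate. The planned stratified analyses depend on sample size, are not said to be pooled into one adjusted effect, and divide 40 to 50 patients by five factors.

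At stake is how well the pilot's efficacy estimate can be read. The protocol wants it as preliminary evidence for a grant application and a larger trial. If no adjusted estimate is pre-specified, any adjustment made later will be open to the charge that its covariates were chosen after seeing the data.

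**Working it through.** **The plan's own figure.** Aim 2 states that 20 per group gives 80% power at alpha 0.05 for standardized differences d from 0.1 to below 0.3. The usual two-sided formula is n per group = 2(1.960 + 0.842)²/d² = 15.70/d². This gives 175 at d = 0.3 and 1,570 at d = 0.1. With 20 per group, power at d = 0.3 is about 16%. The stated size does not reproduce. That is a separate and larger problem; it matters here only because it shows how wide the Aim 2 intervals will be.

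**Inputs.** From the documents: 20 per group (target), 25 per group (maximum), binary primary outcome. Assumed, because the documents give no values: consultation rate 50%, covariate prevalence 30% to 50%, covariate effect on consultation 20 to 50 points.

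**Step 1: chance imbalance under ideal randomization.** Take the difference of two independent Binomial(n, q) counts and find the probability that the proportions differ by 20 points or more.

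| n per arm | q = 30% | q = 50% |
|---|---|---|
| 20 | 22.6% | 26.8% |
| 25 | 16.4% | 20.3% |

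**Step 2: resulting shift.** Shift = imbalance × covariate effect. That is 0.20 × 0.30 = 6 points and 0.20 × 0.50 = 10 points. At an effect of 20 points it is 4 points.

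**Step 3: comparison with sampling error.** SE = √(2 × 0.5 × 0.5/20) = 0.158, so the 95% half-width is 1.96 × 0.158 = 31 points. At 25 per arm the SE is 0.141 and the half-width 28 points. The shift is well inside the interval.

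**Step 4: what adjustment gains.** For one binary covariate, the SE ratio (adjusted/unadjusted) is about √(1 − R²) × √(1 + 1/(2n − 3)), where R² = r²q(1 − q)/[p(1 − p)] and r is the covariate effect. The second factor, the price of estimating one more coefficient, is √(1 + 1/37) = 1.013 at n = 20. With p = q = 0.5, R² = r²:

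- r = 0: 1.013
- r = 0.2: 0.980 × 1.013 = 0.993
- r = 0.3: 0.954 × 1.013 = 0.967
- r = 0.5: 0.866 × 1.013 = 0.878

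Simulation at 20 per arm agrees. The cost is about 2% with robust errors if the covariate is uninformative, and the effect is about nil at 20 points. The SE falls by 2% to 3% at 30 points and by 9% to 12% at 50 points, depending on prevalence. Under no effect the adjusted test rejected in 4% to 5% of trials and the unadjusted test in about 4%; both estimators were unbiased.

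**Step 5: if imbalance is systematic.** Suppose the weekly allocation produced a persistent 20-point gap. With covariate effects of 20, 30 and 40 points, the bias is 4, 6 and 8 points. Dividing by 0.158 gives 0.25, 0.38 and 0.51 standard errors, and the nominal 5% test would reject in about 5.7%, 6.7% and 8.0% of null trials.

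**Step 6: a larger model.** The only insurance classification in the documents has four levels (Aim 1, Definition of Social Vulnerability). Four-level insurance plus a comorbidity count was simulated at 20 per arm, with assumed class shares of 30/30/30/10% and an uninformative comorbidity count. The SE ratio was 1.02 at a 30-point insurance gap and 1.05 to 1.06 with no gap. HC3 robust errors could not be computed in 6% to 7% of trials, because a class held a single patient.

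**The case against.** The strongest reply is that this is a precision option and not an error. A reader might infer that imbalance in groups of 20 biases the telemedicine effect or invalidates the chi-square test. The documents and the arithmetic do not support that. Under true randomization chance imbalance is already part of the unadjusted standard error and type I error, and the 6 to 10 point shift sits inside a half-width of about 31 points. This part of the reply stands.

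It is also fair to say that simple tests suit a pilot whose goals include recruitment and retention rates, that insurance is not ignored because it is one of the planned strata, and that payer class measures surgical coverage only loosely. Consultations outside the health system are counted too, which may weaken the link between insurance and the outcome. The size of that link is assumed throughout.

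Two things remain. First, the repeated-sampling defence presupposes randomization, whereas the protocol describes alternating weeks, which is predictable. Measured differences between arms may then be systematic. A reader might go further and infer that adjustment would repair this allocation. It would not: it addresses only the covariate in the model. Second, conditional strata do not yield one adjusted effect, and nothing else in Aim 2 does.

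**Conclusion.** The point holds as a low-cost improvement. Aim 2 specifies no adjusted estimate of the telemedicine effect, although it collects a covariate that the protocol itself treats as a barrier to surgical care. The unadjusted tests are valid under randomization and need not be replaced. The expected gain is modest: about 3% to 12% off the standard error if insurance shifts consultation by 30 to 50 points, and essentially none at 20 points. In addition, there is partial protection against a measured imbalance from the weekly allocation. These sizes rest on an assumed 50% consultation rate, covariate prevalence of 30% to 50%, and assumed covariate effects. The case does not extend to a model with many covariates or with four-level payer class, which at this sample size gains little or nothing and can fail to fit.

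**What to change.** Keep chi-square or Fisher's exact test as planned. Alongside it, pre-specify one adjusted risk difference for surgical consultation, with arm and a single binary insurance indicator (for example underinsured versus not). Use a linear probability model with small-sample robust standard errors, or a logistic model with standardisation. Use the same indicator in the analysis of time to consultation. Do not use four-level payer class.

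Write the indicator's definition down before outcome data are seen, and choose a split that will fill both categories. The Aim 1 eligibility section puts underinsurance at 7.5% of the primary care population. If that carried over to Aim 2, only 0.075 × 40 = 3 patients would be in the smaller category and the gains above would not apply. The share among socially vulnerable participants is not given. State also what will be reported if one category is nearly empty.

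The report should say that adjustment does not address selection on unmeasured factors under alternating-week assignment.

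Cost: a few lines in the analysis plan, one regression on data already collected, one degree of freedom, and about a 2% larger standard error if insurance does not predict consultation.

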Aim 1: Examine racial disparities in outcomes of PCSL patients with symptomatic GB disease with attention to conditional effects of social vulnerabilities. Hypothesis 1.1: Black patients are less likely to undergo cholecystectomy in the elective setting than White patients. Hypothesis 1.2: Time to consultation will modify the effect of race on elective cholecystectomy. Using PennMedicine data we will perform a retrospective cohort study of PCSL patients diagnosed with symptomatic GB disease between Jan. 1 2020 and Sept. 30, 2022. The primary independent variable will be race. Primary outcome will be cholecystectomy. Secondary outcomes will include time from referral to consultation and treatment, completion of consultation, urgency of operative treatment, and cost. Regression models with interaction terms will be used to evaluate effect modification of additional social vulnerability factors (e.g., ethnicity, primary language, insurance, income) on outcomes.

Aim 2: Comparative effectiveness study of telemedicine consultation for symptomatic GB disease in patients with social vulnerability (SV). Hypothesis 2.1: Recruitment will be feasible in the three-month pilot period. Hypothesis 2.2: Time to telemedicine consultation will be shorter than in-person consultation. We will perform a pilot study of telemedicine vs in-person surgical consultation for patients with SV with symptomatic GB disease seen in PCSL clinics between January and June 2023. Rates of surgical consultation will be compared between groups by consultation type. Secondary outcomes will be examined.

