- In Aim 1, we will not be able to assess patient preference as a reason for undertreatment. We will be able to identify major structural barriers to care (e.g., primary language, insurance etc.). In the pilot study, we will include items on patient preferences (e.g., refusal to see a surgeon or have an operation). This will allow us to gauge the magnitude of this problem in patients with symptomatic GB disease at Penn Medicine. If this is a big problem, we will have to perform additional qualitative studies to determine optimal solutions.
- Telehealth consultation may not be available to the most vulnerable patients. While that was true historically, during the pandemic studies confirmed that telehealth was used widely, especially among those with social vulnerabilities. Moreover, prior to the pandemic, surgical telehealth was used effectively in our system. In the original study, 79% of patients were able to receive telemedicine surgical visits and only 3% were unable due to language or communication barriers.

Future Directions

This study will provide data to develop targeted solutions to achieve surgical health equity at Penn Medicine. For example, in Aim 1, if we discover that underinsurance is the large barrier to treatment, then expanded professional navigation may be the way forward. If mistrust of the system and fears of surgery emerge as barriers to treatment, then peer navigation may be important. Alternatively, if we find that time off work and transportation to visits preclude surgical treatment, then telemedicine consultations (and resultant elective same day surgery rather than emergency in-patient care), may lead us to the path to health equity. We will test this directly in Aim 2. Improving access to care will result in improved patient and provider satisfaction. We will use this information to convene stakeholders within the system to build a Penn Pathway for symptomatic cholelithiasis and biliary colic. Further, this information will provide direction for the design of a larger trial to test multiple additional approaches to overcome barriers to surgical health equity within Penn Medicine that can be scaled across practices and even beyond the confines of our own network. These data will set the stage for high value care bundles to treat patients with social vulnerabilities within Penn Medicine.

REFERENCES

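### Aim 2 assigns whole weeks but tests patients as independent, with no minimum number of weeks per arm; the effect on false positives runs from negligible to severe, depending on how few weeks fill each arm

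*Combined protocol and SAP*

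**What the plan says.** All places are in the Aim 2 part of the combined protocol and SAP unless stated.

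- **Intervention Assignment:** "Pragmatic randomization will be performed by group enrollment in alternating weeks".
- **Exposure:** "Assignment to telemedicine surgical consultation (vs. usual care) during the week of diagnosis". The arm follows from the calendar week, not from an individual allocation.
- **Setting and Participants:** "We anticipate between 2-37 eligible patients per week" and "enrollment will proceed to a maximum of 25 per group". The identification window is 1 April to 30 June 2023. Participation is voluntary, and no consent rate is given.
- **Data Analysis:** "Univariate comparisons to test hypotheses will be performed", using chi-square or Fisher's exact test for categorical outcomes and t or Wilcoxon tests for continuous ones. Stratified analyses use patient characteristics only.
- **Power Calculations:** the plan will "target enrollment of 20 participants per group to achieve a power of 80"% at alpha 0.05.
- **Aim 2 summary, under Aims and Significance:** "Rates of surgical consultation will be compared between groups by consultation type".

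The Aim 2 text does not mention clustering, an ICC, a design effect, calendar time or a minimum number of weeks per arm.

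**The concern.** Patients who enter in the same week share clinic capacity, staffing, appointment availability and referral patterns. If these affect whether a surgical consultation takes place, outcomes within a week are correlated. A patient-level test then counts more independent information than the data hold, and its p-values are too small.

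The size of the problem depends on how many weeks make up each arm. Enrolment stops at a fixed number per group, so fast accrual shortens the calendar span and leaves few weeks per arm. In the extreme of one week per arm, an unusual week cannot be told apart from a telemedicine effect, and no later analysis can separate them.

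The pilot is meant to give preliminary evidence of efficacy and to support a larger grant application. A chance difference between weeks could therefore be carried into the design of the next study.

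**Working it through.** **The plan's own figure.** The plan gives no type I error or design effect for weekly assignment. Its only sample-size figure is 20 per group for 80% power at a standardised difference d from 0.1 to below 0.3. The usual two-sample formula, n = 2(1.96 + 0.84)²/d², gives about 175 per group at d = 0.3. With 20 per group, 80% power needs d of about 0.89. The stated figure therefore does not reproduce. That is a separate matter, and nothing below depends on it.

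**Inputs from the documents.** 2 to 37 eligible per week; target 20 and maximum 25 per group; a 91-day window, which is 13 weeks; alpha 0.05; a binary primary outcome tested by chi-square or Fisher.

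**Assumptions, not in the documents.** ICC between weeks of 0.05 (range 0.01 to 0.10); true consultation proportion of 0.3, 0.5 or 0.7 in both arms; two-sided tests.

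**Step 1: how few weeks could fill an arm?** Consent needed for 25 patients:

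- One week at 37 eligible: 25/37 = 68% (for the target of 20: 20/37 = 54%).
- Two weeks at 37: 25/74 = 34%.
- At the midpoint of the range, 19.5 per week: two weeks need 25/39 = 64%, three weeks 25/58.5 = 43%.
- At 2 eligible per week, 13 weeks give only 26 patients in total, so enrolment would use the whole window.

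**Step 2: normal approximation.** With m patients per week, the design effect is DE = 1 + (m − 1) × ICC, and the actual type I error is 2 × [1 − Φ(1.96/√DE)]. For one week of 25 per arm:

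- ICC 0.01: DE 1.24, error 7.8%.
- ICC 0.05: DE 2.20, error 18.6%.
- ICC 0.10: DE 3.40, error 28.8%.

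**Step 3: exact check.** Weekly counts follow a beta-binomial distribution with the stated ICC. Every possible 2×2 table is enumerated, and the probability of p < 0.05 is summed when the arms do not differ. The chi-square test is uncorrected. Ranges are over the three assumed proportions.

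| Weeks per arm × patients per week | Chi-square, ICC 0.05 | Fisher, ICC 0.05 | Chi-square, ICC near 0 | Fisher, ICC near 0 |
|---|---|---|---|---|
| 1 × 25 | 20.6-22.0% | 13.5-15.5% | 5.4-6.5% | 2.3-3.3% |
| 2 × 12 | 12.2-13.3% | 7.6-8.2% | 5.2-6.0% | 2.6-2.9% |
| 6 × 4 | 7.0-7.9% | 3.8-4.3% | 5.2-6.0% | 2.6-2.9% |

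**Step 4: what a week-level analysis needs.** With the order randomised within pairs of weeks, k pairs give 2^k arrangements, and the smallest two-sided permutation p-value is 2/2^k. Five pairs give 2/32 = 0.0625, which can never reach 0.05. Six pairs give 2/64 = 0.031. Six pairs occupy 12 of the 13 weeks.

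**Step 5: cost in precision.** With 4 per week and ICC 0.05, DE = 1 + 3 × 0.05 = 1.15, and √1.15 = 1.072. The widening relative to a patient-level interval with critical value 1.96 is:

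- Unpaired, 12 weeks (10 degrees of freedom, t = 2.228): 1.072 × 2.228/1.96 = 1.22.
- Paired, six pairs (5 degrees of freedom, t = 2.571): 1.072 × 2.571/1.96 = 1.41, before any gain from pairing.

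**The case against.** The best defence is that the worst case stacks several unlikely conditions. The figure of 37 counts eligible patients, not enrolled ones, and is the top of a wide range. Filling each arm in one week needs two peak weeks with about 68% consent. The plan provides for slow recruitment with a fallback approach, and the Aim 2 summary expects a three-month period. If enrolment spreads over the window, inflation is small, and Fisher's test, which the plan allows, stays below 5% in the six-week case at ICC 0.05. The study is also a pilot whose goals include recruitment, retention and variance estimates. All of this stands and limits the severity. It does not dispose of the point, because hypothesis tests are still planned and nothing in the plan prevents few weeks per arm.

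A reader might infer two stronger conclusions that the documents do not support.

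- *That the planned test has a false-positive rate of about 19% and cannot separate week from treatment.* That figure is the normal approximation for one week of 25 per arm at an assumed ICC. It is neither the expected case nor a ceiling, and full confounding needs exactly one week per arm.
- *That the plan intends an as-treated analysis in which about a fifth of patients switch group.* The phrase "Rates of surgical consultation will be compared between groups by consultation type" is in an aims summary. The Exposure paragraph defines groups by assignment, and a patient with no consultation has no type, so the assigned reading is the workable one. The Limitations statement that "79% of patients were able to receive telemedicine surgical visits" describes a different, pre-pandemic population and does not predict switching here. What remains is a conflict of wording.

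**Conclusion.** The mismatch holds: weeks are assigned, patients are analysed, and no minimum number of weeks per arm protects the comparison. At an assumed ICC of 0.05, the type I error of the primary comparison runs from 7-8% (chi-square) or about 4% (Fisher) with six weeks of 4 per arm to 21-22% or 13-16% with one week of 25 per arm. Over an ICC of 0.01 to 0.10, the one-week case runs from 7.8% to 28.8% by the normal approximation. Where the study would fall depends on the ICC and the consent rate, and the documents give neither. The same dependence affects the t and Wilcoxon tests of the secondary outcomes, which were not quantified. The plan should be changed, because the remedy is cheap and the worst case cannot be repaired after enrolment.

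**What to change.** 1. **Groups compared.** State that all enrolled patients are analysed in the week group to which they were assigned, and bring the Aim 2 summary wording into line with the Exposure paragraph.
2. **Unit of analysis.** Test with week as the cluster, either by a week-level comparison with t critical values or by permuting week labels over at least six pairs of weeks. Alternatively, present the between-group comparison as descriptive, without p-values.
3. **Spread of enrolment.** Require at least six weeks per arm within the 13-week window. A flexible weekly ceiling would do this: 4 places per week over six weeks gives 24 per arm, with unused places carried forward so that slow weeks can be made up. A rigid cap of 4 would risk under-enrolment. Log every eligible and willing patient, including those above the ceiling, so that the recruitment rate can still be estimated.
4. **Order.** Randomise which arm comes first within each pair of weeks, in place of fixed alternation.

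**Cost.** Reported intervals become about 1.2 times wider (unpaired) to 1.4 times (paired, before any gain from pairing) at ICC 0.05. Enrolment must run for about 12 weeks even if patients are plentiful, and a screening log is needed. The descriptive option avoids the test but gives up the formal hypothesis test.
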